## 1. EXECUTIVE SUMMARY

### Introduction

Colorectal cancer (CRC) is one of the most common malignancies in Western nations, and the second most common in Spain after lung cancer in men and breast cancer in women. Its incidence is estimated at 25,000 new cases per year, and it is the second leading cause of cancer death.

Although the efficacy of CRC screening in the prevention of this cancer is well established, the most appropriate procedure for screening has not yet been identified.

### Primary objective

To measure CRC-specific mortality at 10 years after screening using biennial faecal immunochemical testing (FIT) compared to screening by one-time colonoscopy in an average-risk population (asymptomatic individuals aged 50-69 years with no personal or family history of CRC).

### Study design

A pragmatic, non-inferiority, multicentre, randomised, controlled trial in eight Autonomous Regions of Spain (Aragon, Canary Islands, Catalonia, Galicia, Madrid, Murcia, Basque Country, and Valencia).

### Methodology

Inclusion criteria: Asymptomatic men and women between the ages of 50 and 69.

Exclusion criteria: 1) Having previously undergone CRC screening within the prescribed period; 2) Belonging to high-risk groups due to family history (hereditary nonpolyposis colorectal cancer, familial adenomatous polyposis, other hereditary polyposis syndromes, first-degree relatives with CRC) or personal history (inflammatory bowel disease, adenoma, or prior CRC); 3) Symptoms suggestive of colorectal disease; 4) Having undergone a total colectomy; or 5) Individuals suffering from a serious illness.

### Study groups

*Group 1:* Screening using biennial FIT (latex agglutination, OC-Sensor®, cut-off point: 75 ng Hb/ml), and performance of colonoscopy in patients with a positive result.

*Group 2:* Screening using one-time colonoscopy.

The study design allowed for cross-over between both screening strategies.

### Sample size calculation

With an alpha risk of 0.025 and a beta risk of 0.20, using one-sided test of proportions, 27,749 subjects are required in each trial arm (total: 55,498) accepting a non-inferiority condition if the absolute difference was below 1.6% in the CRC-specific mortality rate at 10 years according to the intention to screen analysis (primary objective of the study).

## 2. BACKGROUND AND CURRENT STATUS OF THE ISSUE

Colorectal cancer (CRC) is the second most common cause of cancer death in Spain, accounting for more than 11,000 deaths annually. Its rate of incidence makes it the second most common cancer after lung cancer in men and breast cancer in women, but it is the most common cancer if figures for both genders are combined, with more than 25,000 new cases detected each year (1).

The mean survival rate for CRC in Spain is only 48% at 5 years after diagnosis (2). This may be because diagnosis is made late, in most cases as a result of a lack of screening programmes.

Several prestigious medical societies and clinical guidelines based on scientific evidence recommend screening for all individuals over the age of 50 even if no additional risk factors are present, as well as for members of high-risk population groups (hereditary CRC syndromes, individuals with first-degree relatives with CRC, and patients suffering from inflammatory bowel disease) (3-12). For screening in high-risk populations, the strategy of choice is colonoscopy, performed at various intervals depending on the clinical situation (6,12). However, it is not known which screening method (annual or biennial faecal occult blood testing [FOBT], sigmoidoscopy every 5 years, or colonoscopy every 10 years) is the most suitable for the average-risk population.

Of all the possible strategies, the most evaluated to date is annual or biennial FOBT screening. Several randomised controlled trials have shown that FOBT screening with a chemical test (guaiac) reduced mortality from CRC by approximately 15-30% (13-15) and also reduced its incidence (16). However, this method has been disputed because of its low sensitivity, with a detection rate of 30-50% in a single round of screening for CRC (15,17), and of less than 20% for advanced adenoma (18,19). Other disadvantages of screening with the guaiac-based FOBT method are that it needs to be repeated every 1-2 years, that it requires dietary restrictions to ensure the reliability of the test, and that three consecutive samples must be collected, thereby greatly reducing compliance. On the other hand, there are faecal immunochemical tests (FIT) that are more sensitive than chemical methods (20). Such methods specifically detect human haemoglobin, and therefore do not require dietary restrictions and only need a single sample to be taken. However, they have been insufficiently tested in Western countries, and there are no studies on the cost-effectiveness of CRC screening using this procedure.

In the past 15 years several pilot studies have been carried out in Spain for early detection of CRC in average-risk populations (21-25). Most of them used the chemical FOBT method as a screening test, followed by colonoscopy in individuals with a positive result. In total, these studies included more than 12,000 participants, with an average participation rate of 56% and an average detection rate of early stage CRC of 80%. Although these studies are not comparable from the methodological point of view, and were performed at different times, the results suggest an acceptable level of participation in the Spanish population, and high efficacy in the early detection of CRC. However, no studies have been conducted in Spain assessing the efficacy of screening in terms of mortality or incidence over the long-term.

In a recent study conducted in Tenerife (25), the acceptance, efficacy, and cost-effectiveness of a new FIT (latex agglutination, OC-Light®) was compared to the hemoFEC® chemical test for the detection of advanced adenoma and CRC. The study showed that the immunological method is more sensitive than the chemical test for detection of advanced adenoma (51% vs. 18%), CRC (100% vs. 52%) or both (57% vs. 22%). Specificity with the immunological method was 97% for advanced adenoma, 93% for CRC, and 95% for both, while with the chemical test it was 97% for

either advanced adenoma or CRC, and 98% for both. This study also showed that the probability of detecting advanced cancers (advanced adenoma or CRC) in individuals with a positive immunological test (OR: 13; 95% CI: 6.1-27.7) was four times higher than that for those in whom the chemical test was positive (OR: 3.17; 95% CI: 1.98-5.07). The immunological method was also more cost-effective than the chemical test in the detection of CRC or advanced adenoma. The chemical FOBT test achieved a cost-effectiveness ratio of € 3,573/QALY gained, reducing CRC-caused mortality by 20%, while for the immunological test the ratio was € 2,224/QALY gained, with a reduction in mortality of 52%. These data suggest that the FIT should replace the chemical method in future CRC screening campaigns in average-risk population.

Colonoscopy is the most accurate method that exists for the early detection and prevention of CRC. Although studies evaluating the effect of screening with this test on CRC-caused mortality in average-risk populations have not yet been published, its implementation is recommended based on the following evidence: 1) studies have demonstrated that colonoscopy with polypectomy reduces the incidence of CRC by 40-90% (27,28); 2) At least two case-control studies suggest that screening by flexible sigmoidoscopy significantly reduces the risk of death from distal CRC (29,30), an effect that lasts for more than 5 years (30) which has enabled extrapolation of its effectiveness to colonoscopy; 3) The prevalence of adenomas in cross-sectional studies of screening by colonoscopy is twice that observed for sigmoidoscopy (18,19,31,32), with colonoscopy also found to be more sensitive than the barium enema or virtual colonoscopy for detecting polyps and CRC (26); 4) Approximately two out of three patients with advanced cancers of the proximal colon do not show neoplasia distal to the splenic flexure, meaning that it would not be detectable in screening by sigmoidoscopy (33,34). This is particularly relevant if one considers that 40% of CRCs are located proximal to the splenic flexure (35).

An additional benefit of colonoscopy every 10 years compared to other screening strategies in an average-risk population is that it allows a long period of protection, which can help improve compliance in the population. It also facilitates diagnosis and treatment in one session, which decreases the risk of the loss of patients to follow-up that occurs with tests that are purely diagnostic.

The primary limiting factors for the use of colonoscopy in screening an average-risk population are its invasive nature, including a possible risk of potentially serious complications such as perforation or post-polypectomy bleeding (1-2 per 2,000 examinations), and a higher cost than other screening methods such as the FOBT test.

Despite the proven beneficial effect of secondary prevention on morbidity and mortality from CRC, there are significant obstacles that hinder the implementation of large-scale CRC screening programmes. First, there is still no agreement as to what constitutes an optimal screening strategy. Secondly, there is little compliance with them by the target population. This is due mainly to a significant lack of information among the target population, and among healthcare managers and staff themselves (36-38). Finally, the organisation and resources needed to ensure the safety and efficacy of a programme of this nature are not currently available.

An essential requirement for the implementation of any population screening programme for a particular disease is to be cost-effective. Several studies have confirmed that CRC screening is cost-effective regardless of the strategy applied (39-41), with the cost in terms of quality-adjusted life years (QALY) being lower than screening for other cancers such as breast or cervical cancer (40). These findings were corroborated in a recent analysis by the Evaluation and Planning Unit of the Canary Islands Health Service (unpublished data), which found that the costs of CRC screening using FIT or colonoscopy every 10 years would be significantly lower

(€ 2,500/QALY and € 2,300/QALY, respectively) than screening for breast (€ 18,489/QALY), cervical (€ 18,646/QALY) or prostate cancers (€ 12,647/QALY). It is worth noting that the National Institute for Health and Clinical Excellence (NICE) has recently established that any health intervention that costs less than € 30,000/QALY should be considered to be very acceptable from the standpoint of cost-effectiveness (42) and has, therefore, recommended its implementation.

Given that CRC is a high-priority health issue, and that sufficient evidence exists to show that it is a preventable disease with reasonable economic costs if diagnosed early, the Council of the European Union established guidelines in 2003 (43) so that population screening for CRC would be included as a priority in the health plans of member states. For that reason, the national health plan of the Spanish Ministry of Health and Consumer Affairs includes population screening for CRC as a priority as part of its comprehensive cancer plan (PICa), which is to be implemented before 2007 (43).

The Spanish Association of Gastroenterology (AEG) believes that, in order to reduce the mortality and incidence of CRC in Spain, various actions must be taken, among which are publicising the CCR prevention strategies, promotion of their implementation, establishment of mechanisms for assessment, improvement of the efficiency and quality of care levels involved and promotion of comprehensive care for patients with this cancer. This Association, therefore, proposes to conduct a multicentre, controlled study with a scope that covers several Autonomous Regions to establish the efficacy and efficiency of the two principal screening options in the average-risk population.

### **3. OBJECTIVES**

#### **3.1. Primary objective**

- To assess CRC-specific mortality at 10 years after screening using a FIT method biennially compared to screening by one-time colonoscopy in an average-risk population (asymptomatic individuals aged 50-69 with no personal or family history of CRC).

#### **3.2. Secondary objectives**

- To compare diagnostic yield and detection rate of CRC and/or advanced adenomas in each screening strategy at the completion of the first round.
- To compare the participation rate in each screening strategy at the completion of the first round, and identify the factors influencing it (i.e. demographics, personal and familial characteristics, socio-economic status, etc.).
- To compare overall diagnostic yield and detection rate of CRC and/or advanced adenomas in each screening strategy at 10 years.
- To compare the overall adherence rate in each screening strategy at 10 years, and identify the factors influencing it.
- To assess the cost-effectiveness of each screening strategy.
- To assess the rate of serious complications in each screening strategy, both at the completion of the first round and overall at 10 years.
- To compare CRC incidence in each screening strategy at 15 years.

#### **3.3. Additional objectives**

Each Autonomous Region, hospital, and/or health centre participating in the study can propose additional objectives to be performed in its individual data sets. Any proposal should be approved by the Executive Committee of the COLONPREV study.

## 4. STUDY METHODOLOGY

### 4.1. Study type

Pragmatic, non-inferiority, multicentre, randomised and controlled.

### 4.3. Target population

Inclusion criteria: Asymptomatic men and women between 50 and 69 years of age. This cutoff of age is the recommended by the Spanish Screening Network for the implementation phase of the Spanish CRC screening program. Thereafter, it is planned to increase this age cutoff to 74 years when the screening program will be extended to the whole country (unfortunately, this stage has not been accomplished at the end of COLONPREV study).

Permanent exclusion criteria: All individuals who meet any of the following conditions will be permanently excluded:

- Personal history of inflammatory bowel disease, colorectal polyps, colorectal adenoma or CRC.
- Family history of familial adenomatous polyposis syndromes or other hereditary polyposis syndromes, hereditary nonpolyposis colorectal cancer (diagnosed by the presence of germline mutation in DNA repair genes and/or meeting the Amsterdam II criteria), 2 or more first-degree relatives with CRC or 1 first-degree relative with CRC diagnosed before the age of 60.
- Severe comorbidity that involves a poor short-term prognosis (disease with a mean life expectancy of less than 5 years) or chronic disease that involves major limitation of physical activity (performance status  $\geq 2$ ).
- Individuals who have had a total colectomy.

Temporary exclusion criteria: All individuals who meet any of the following conditions will be temporarily excluded:

- Those who have undergone any of the examinations used in CRC screening, regardless of the reason, within the periods specified: history of FOBT screening in the past 2 years, or sigmoidoscopy or colonoscopy within the past 5 years (as long as its validity is documented) (to avoid this eventuality we will seek to conduct the study in a healthcare setting in which the population has not been screened previously). Such individuals may enter the study after the time periods mentioned have expired.

- Those showing symptoms suggestive of colorectal disease (rectal bleeding, altered frequency of bowel movements, constitutional symptoms, anaemia). These individuals may enter the study once their condition has been studied and a colorectal cancer or other pathology that would constitute a cause of permanent disqualification has been excluded, and if any of the above-mentioned tests were performed, once the periods mentioned in the previous section have expired.

#### 4.4. Study groups, randomisation, and stratification

Asymptomatic men and women aged 50 to 69 years from each participating Autonomous Region will be identified through the corresponding Community Health Registry (CHR) for enrolment into this study. Randomisation will be carried out prior to invitation, with computer-generated lists in blocks of 4 (block randomisation) from the list of health cards, after having previously grouped individuals by household (specified by street address, floor, and apartment number) (see Processes of selecting and inviting the population to be screened section).

All eligible patients will be randomised (1:1 ratio) to the two study groups:

Group 1: Screening by biennial FIT (latex agglutination, OC-Sensor®, cut-off point: 75 ng Hb/ml, corresponding to 15 µg Hb/g of feces), and colonoscopy (after no more than 1 month) for patients with a positive result. Determination of FIT will be made using a single faecal sample, without dietary restriction or interruption of normal treatment of the individual, although the habitual use (>1 month) or recent use (last 7-15 days) of NSAIDs, aspirin, anti-platelet drugs and anticoagulants will be recorded. The above-mentioned cut-off point was used in the baseline round; in subsequent rounds, we decided to modify the cut-off to 20 µg Hb/g of feces since it is the one accepted in the Spanish population-based CRC screening program.

Group 2: Screening by one-time colonoscopy. The ongoing use (>1 month) or recent use (last 7-15 days) of NSAIDs, aspirin, anti-platelet drugs and anticoagulants will also be recorded.

Individuals in Group 1 or Group 2 who do not agree to the type of testing assigned to them may require receiving the alternative test and must still be followed up in order to carry out efficacy analysis according to the intention to screen analysis. The choice of the alternate test will not be actively offered to individuals invited to the study and, accordingly, COLONPREV is not considered a study of sequential screening test offers.

Information on the long-term status of individuals in Group 1 or Group 2 who do not agree to participate in the study will be obtained through population-based registries at the completion of the trial in order to assess efficacy according to the intention to screen analysis.

#### 4.5. Sample size calculation

##### Considerations for calculation of the sample

Since there are no study examining the effect of screening with the strategies proposed in our trial on CRC-caused mortality, the calculation of the sample in this case must be based on hypothetical studies of cost-effectiveness that analyse the expected reduction in risk of mortality with biennial FIT or colonoscopy every 10 years. Furthermore, the calculation should be adjusted, when possible, to the local conditions where the strategies are to be implemented. In that sense, it is important to note that no study on this subject have yet been published in Spain.

Recently, the Evaluation and Planning Unit of the Canary Islands Health Service has conducted a study of this type based on real data for sensitivity and specificity of the tests in our setting. For a hypothetical population of 100,000 asymptomatic individuals aged 50, the estimated mortality reduction brought about by FIT is 51% and involves a cost of € 2,101/QALY. For the strategy of colonoscopy, the estimate is a reduction in mortality of 75% at a cost of € 2,188/QALY.

With an alpha risk of 0.025 and a beta risk of 0.10 using one-sided test of proportions, 27,749 subjects are required in each arm of the clinical trial (total: 55,498) accepting a non-inferiority condition if the absolute difference was below 1.6% in the CRC-specific mortality rate at 10 years according to the intention to screen analysis and with an expected overall compliance of 30%.

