### Intention-to-treat

Cumulative incidence curves for the invitation arms will be estimated with the Kaplan-Meier estimator, considering the period from the day of randomization to the end of follow-up. The Kaplan-Meier estimator with daily outcome events will be used to compute the probability (risk) of the outcome during the period. For CRC incidence and mortality, non-CRC events will be considered as censoring events. We will calculate the 10-year risk differences and risk ratios between the trial arms, whereas 95% confidence intervals (95% CI) will be computed using the normal approximation.

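### The same 27,749 per arm is given with 80% power in the executive summary and 90% power in section 4.5; at least one of these is wrong

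*Combined protocol and SAP*

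**What the plan says.** The sample size is stated twice, both times in current text.

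- Executive summary, Sample size calculation: "With an alpha risk of 0.025 and a beta risk of 0.20, using one-sided test of proportions, 27,749 subjects are required". The figures are "required in each trial arm (total: 55,498"), and the criterion is "accepting a non-inferiority condition if the absolute difference was below 1.6"% for CRC-specific mortality at 10 years, by intention to screen.
- Section 4.5, Considerations for calculation of the sample: "With an alpha risk of 0.025 and a beta risk of 0.10 using one-sided test of proportions, 27,749 subjects are required". The figures are "required in each arm of the clinical trial (total: 55,498"), with the same margin, endpoint and analysis. This version adds "with an expected overall compliance of 30"%.

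Section 4.5 also cites a modelling study with mortality reductions of 51% for FIT and 75% for colonoscopy. Neither place gives the expected 10-year CRC mortality, says what true difference between arms was assumed, or explains how compliance entered the calculation. Power is mentioned nowhere else.

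**The concern.** The two statements agree on every input they share except beta, and they give the same required sample. Required sample size depends on beta, so both cannot be correct for one set of planning assumptions.

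This matters mainly if the trial fails to show non-inferiority. A reader would then ask whether the trial was planned at 80% or 90% power. The documents give two answers, and the reader cannot work out the right one because the event rate and the assumed difference are missing.

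The reach of the problem is limited. Section 7 (Intention-to-treat) plans the analysis as "We will calculate the 10-year risk differences and risk ratios between the trial arms, whereas 95% confidence intervals (95% CI) will be computed" by a normal approximation, and beta plays no part in it.

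**Working it through.** **Inputs from the documents.** One-sided alpha 0.025; beta 0.20 (executive summary) or 0.10 (section 4.5); margin 0.016 absolute; 1:1 allocation (section 4.4); 27,749 per arm; compliance 30% and reductions of 51% and 75% (section 4.5). All event rates below are assumptions, because none is stated.

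**1. Effect of beta alone.** With the other inputs fixed, n is proportional to (z_alpha + z_beta)².

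- 80% power: (1.95996 + 0.84162)² = 7.8489
- 90% power: (1.95996 + 1.28155)² = 10.5074
- Ratio: 10.5074 / 7.8489 = 1.3387

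If 27,749 gives 80% power, 90% needs 27,749 × 1.3387 ≈ 37,148 per arm. If 27,749 gives 90%, 80% needs 27,749 / 1.3387 ≈ 20,728. A gap of a third is not rounding.

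**2. Can 27,749 be reproduced?** Not uniquely, since the event rate is missing. Take equal true rates p, unpooled variance, independent individuals and no compliance adjustment:

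n = 2p(1−p)(z_alpha + z_beta)² / 0.016²

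This is largest at p = 0.5:

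- 80%: 0.5 × 7.8489 / 0.000256 = 15,330
- 90%: 0.5 × 10.5074 / 0.000256 = 20,523

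Both are below 27,749. Reaching 27,749 would need p(1−p) = 0.453 (80%) or 0.338 (90%), and p(1−p) cannot exceed 0.25. On these inputs the lowest power at 27,749 occurs at p = 0.5: SE = √(0.5/27,749) = 0.004245, and Φ(0.016/0.004245 − 1.960) = Φ(1.809) = 96.5%. At assumed rates of 0.3% to 5% power is about 100%. Neither stated beta matches this reading.

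**3. Does the 30% compliance reconcile the two?** Four ways of using it, each solved for the rate at which 27,749 has the stated power:

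| Use of compliance and true difference | Rate for beta 0.20 | Rate for beta 0.10 |
|---|---|---|
| Equal rates, n inflated by 1/0.30 | 16.2% | 11.5% |
| Equal rates, n inflated by 1/0.30² | 4.25% | 3.14% |
| 51% and 75% reductions as true effect, full compliance | 5.29% | 5.11% |
| 51% and 75% reductions diluted to 30% compliance | 12.3% | 11.2% |

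The rates are common arm rates in the first two rows and unscreened mortality in the last two. For the second row: 27,749 × 0.09 = 2,497, so p(1−p) = 2,497 × 0.000256 / (2 × 7.8489) = 0.0407 for beta 0.20, and 0.0304 with 10.5074 for beta 0.10. In the last row the arm rates for unscreened mortality m are m(1 − 0.153) and m(1 − 0.225), a difference of 0.072m; for m of 0.3% to 5% power is about 100%.

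No row has one rate that serves both betas.

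**4. Could the summary assume full compliance and section 4.5 assume 30%?** At the 5.29% unscreened mortality where full compliance gives 80% power, 30% compliance gives about 100%, not 90%. Dilution shrinks the difference between arms while the margin stays at 1.6%, so power rises well past 90%.

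**The case against.** The conflict and the arithmetic are not in dispute. The case against giving the point weight has four parts.

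- **That both betas may be wrong is conjecture.** The calculation that excludes both leaves out a compliance adjustment, although section 4.5 says compliance was expected to be 30%. With a 1/0.30² inflation, or with the modelled reductions at full compliance, either beta can be matched by some rate. This stands as a limit: the documents prove that at least one figure is wrong, and leave open whether both are. It does not help the plan, because each route needs a different rate for each beta.
- **The 96.5% floor assumes independent individuals.** Sections 4.4 and 4.6 group people by household before randomisation. At the 50% rate behind the floor, an assumed design effect of 1.35 lowers power to 90.0%, and one of 2.0 to 76.0%. The condition is real, but it matters little at realistic CRC mortality.
- **Little turns on it now.** Section 8 puts study completion in December 2021 and the main analyses in June 2024, so no design decision remains, and the confidence interval conveys the precision obtained. That limits the consequence. It does not make two contradictory statements about the primary endpoint acceptable.
- **This is an inconsistency, not a shown miscalculation.** That is fair: the planning calculation is not in the documents, so no step of it can be faulted. The conflict shows only that the same result is attributed to two different inputs.

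**Conclusion.** The concern holds. With all other inputs fixed, 27,749 per arm cannot be the required sample for both 80% and 90% power; the two differ by a factor of 1.339, or 37,148 against 27,749, or 27,749 against 20,728. That conclusion needs no assumed event rate. The compliance figure in section 4.5 does not remove the conflict under any of the uses tried.

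Whether either beta is right cannot be settled from the documents. On the margin as written, with equal true rates, independent individuals and no compliance adjustment, neither matches, since power is at least 96.5%. Other uses of compliance can match one beta at a time, at rates the plan does not state.

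This is a reporting conflict about planned power. It should be corrected, but it does not affect the analyses or the number recruited.

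**What to change.** Recover the original planning calculation. In section 4.5, state its assumed 10-year CRC mortality, assumed true difference, margin and compliance adjustment. Then give, in both section 4.5 and the executive summary, the one power that 27,749 per arm delivers under those assumptions. If the calculation cannot be recovered, say so plainly rather than choosing one of the two betas.

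Do not add enrolment on this account, and do not fill the gap with power computed from the observed rates.

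The cost is a search of the planning files and a short correction in two places. The corrected power may be lower or higher than a figure now stated.

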## 8. CHRONOGRAM

The study will be developed according to the following chronogram:

- Initial meeting: October 28th, 2008
- Formative meeting for data-collectors and other auxiliary staff: December 12th, 2008
- Informative campaign launched by the Spanish Alliance for CRC Prevention and involving national and local media: from November 2008 to March 2009
- Recruitment period will be initiated in June 2009
- Quality Committee meetings will be held during the first round according to the following calendar:
  - June 12th, 2009
  - December 11th, 2009
  - June 11th, 2010
  - December 10th, 2010
- First round of screening will be finished in June 2011
- First follow-up meeting (first-round interim analysis): July 2011
- Other follow-up meetings will be held regularly during the study period, in a biennial basis (date will be announced properly)
- Other Quality Committee meetings will be held regularly during the study period, in a annual basis (date will be announced properly)
- Completion of the study: December 2021
- Analyses of main end point results (i.e. CRC mortality and incidence and any-cause mortality at 10 years): June 2024
- Follow-up conference calls among members of the Executive Committee will be held periodically, every four months, during the study period.

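### The 1.6-point non-inferiority margin does not fit 27,749 per arm at any realistic CRC death risk, and used as the decision rule it would accept several-fold excess CRC mortality

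*Combined protocol and SAP*

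**What the plan says.** The trial is declared non-inferiority (Executive Summary, Study design; section 4.1). The Executive Summary and section 4.5 give the same criterion, "accepting a non-inferiority condition if the absolute difference was below 1.6% in the CRC-specific mortality rate at 10 years", and the same size: 27,749 per arm, 55,498 in total.

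The two places differ on power. The Executive Summary has "With an alpha risk of 0.025 and a beta risk of 0.20". Section 4.5 has "With an alpha risk of 0.025 and a beta risk of 0.10 using one-sided test of proportions".

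Section 4.5 also adds a compliance assumption, "with an expected overall compliance of 30" per cent, without saying how it enters the formula. It cites a model in which FIT lowers CRC mortality by 51%, and "For the strategy of colonoscopy, the estimate is a reduction in mortality of 75" per cent. No expected 10-year CRC death risk is given for either arm or for unscreened people, and the margin is not justified.

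For the primary analysis, section 7 (Intention-to-treat) says "We will calculate the 10-year risk differences and risk ratios between the trial arms", with 95% confidence intervals. It states no margin and no rule for concluding non-inferiority.

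**The concern.** CRC death within 10 years is uncommon in asymptomatic people aged 50-69. An absolute margin of 1.6 points is therefore likely to exceed the event risk itself, and a margin that wide should need a few hundred people per arm, not 27,749. Either the margin or another input is misstated.

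This matters because 1.6% is the only success threshold for the primary endpoint. A reader who looks for the non-inferiority criterion will find nothing in section 7 and must take it from the sample-size text. If it is applied as printed, FIT could be called non-inferior with far more CRC deaths than colonoscopy, or with no screening effect at all.

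**Working it through.** **Inputs from the documents.** One-sided alpha 0.025; power 80% (Executive Summary) or 90% (section 4.5); margin d = 0.016; n = 27,749 per arm, 1:1; compliance 30%; modelled reductions 51% (FIT) and 75% (colonoscopy). **Assumed:** the 10-year CRC death risk p, or u if unscreened.

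**1. Trying to reproduce 27,749, equal risks, no compliance adjustment.**
n = 2p(1-p)(z₀.₉₇₅ + z_power)²/d², where the squared term is 7.849 (80%) or 10.507 (90%).

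| p | n, 80% | n, 90% |
|---|---|---|
| 0.3% | 184 | 246 |
| 0.5% | 306 | 409 |
| 1.0% | 608 | 813 |
| 50% (maximum) | 15,330 | 20,523 |

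Reaching 27,749 would need p(1-p) = 27,749 × 0.016²/(2 × 10.507) = 0.338 at 90% power, or 0.453 at 80%. The largest possible value is 0.25, so there is no solution. This step uses no outside figure.

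**2. Bringing in compliance and the modelled reductions.** The method is not stated, so several were tried. N/0.09 is N/0.30², which equals shrinking the margin to 0.30 × 1.6 points. The table shows the death risk at which N becomes 27,749.

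| Approach | 80% | 90% |
|---|---|---|
| Equal risks, N/0.30 | 16.2% | 11.5% |
| Equal risks, N/0.09 | 4.3% | 3.1% |
| 51% vs 75% diluted to 30% compliance, no inflation (u) | 12.3% | 11.2% |
| 51% vs 75% undiluted, no inflation (u) | 5.3% | 5.1% |
| 51% vs 75% undiluted, N/0.09 (u) | 3.1% | 2.8% |

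In the diluted row, FIT risk is (1 - 0.30 × 0.51)u = 0.847u and colonoscopy risk is (1 - 0.30 × 0.75)u = 0.775u, a true difference of 0.072u. The lowest value found under any variant is 2.8%.

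**3. Is 2.8% realistic?** Section 2 gives just over 11,000 CRC deaths a year in Spain at all ages. Suppose all of them, for ten years, fell in people aged 50-69 at the start. With 6-10 million such people (assumption), the risk would be 110,000/6,000,000 = 1.8% down to 110,000/10,000,000 = 1.1%. Reaching 2.8% would need that group to number only 110,000/0.028 = 3.9 million. Section 4.3 also excludes people with previous CRC or adenoma.

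**4. What the printed margin would accept.** The pass limit solves pF - pC + 1.96√[pF(1-pF)/n + pC(1-pC)/n] = 0.016 at n = 27,749.

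| Colonoscopy risk pC (assumed) | Largest passing FIT risk | Ratio | Deaths, FIT vs colonoscopy |
|---|---|---|---|
| 0.2% | 1.64% | 8.2 | 456 vs 55 |
| 0.3% | 1.73% | 5.8 | 481 vs 83 |
| 0.5% | 1.92% | 3.8 | 532 vs 139 |
| 1.0% | 2.39% | 2.4 | 662 vs 277 |

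The margin itself is 27,749 × 0.016 = 444 extra CRC deaths in one arm. The 95% CI half-width at equal risks, 1.96√[2p(1-p)/n], is 0.09 points at 0.3% and 0.17 points at 1.0%. The margin is thus about 10 to 18 times the trial's precision.

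**5. Would an arm with no screening effect pass?** Take pF = u and pC = 0.775u. Then P(pass) = Φ((0.016 - 0.225u)/SE - 1.96). This is above 99.9% for u up to 3%, 78% at u = 5% and 3% at u = 7%.

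**6. Can the intended margin be inferred?** No. Without inflation at 90% power, 27,749 fits a margin of 0.10 points at p = 0.13%, 0.16 at 0.34%, 0.20 at 0.53% or 0.25 at 0.83%. At 80% power, 0.16 points fits at 0.455%. A superiority formula for 51% vs 75% at full compliance also gives 27,749, at u = 0.36% (80%) or 0.49% (90%), with no margin at all.

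**The case against.** The documents give no 10-year CRC death risk, so the word realistic rests on an assumption. What the documents prove alone is narrower: no solution exists with equal risks and no compliance adjustment. Since section 4.5 does mention compliance, an adjustment cannot be excluded. That is right, and it is why the full implied range from 2.8% upward is shown. Even its lowest value lies above a deliberately generous ceiling built from the plan's own death count.

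The several-fold figures also depend on the assumed risk. The largest passing ratio falls to 1.9 at 1.5%, 1.7 at 2% and 1.4 at 3%. Under the plan's own inputs such results are unlikely: a no-effect arm at 30% compliance has a ratio of 1/0.775 = 1.29, and even full compliance against no effect gives 1/0.25 = 4.0. This stands as a statement about what is likely to be observed. It does not rescue the criterion, because a threshold that admits those ratios also passes a no-effect arm almost surely (step 5).

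Finally, section 7 never applies 1.6%, and the planned risk ratio would reveal any excess. Both points are true, and the precision in step 4 does not suggest that the trial is too small. But a declared non-inferiority trial needs a criterion, and this is the only one written down.

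**Conclusion.** The concern holds. The margin, N and compliance do not reproduce, and the two beta values for one N cannot both be right with the other inputs unchanged. With equal risks and no inflation, the mismatch is purely internal: at most 20,523 against 27,749. With compliance or the modelled reductions included, it rests on the 10-year CRC death risk being below 2.8%, which the national death count supports for any 50-69 population above about 3.9 million.

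As a decision rule, 1.6 points would accept observed death ratios of 2.4 to 8.2 at assumed colonoscopy-arm risks of 1.0% to 0.2%. It could not separate FIT from no screening at unscreened risks up to 3%. Because this is the primary endpoint's only threshold, it must be corrected before any non-inferiority conclusion is drawn.

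**What to change.** Recover the original calculation record. From it, correct the Executive Summary and section 4.5 to state the margin actually used and its units, the expected 10-year CRC death risk in each arm, how 30% compliance enters, and one beta. Do not derive the margin from N or from observed results. Step 6 shows that several margins fit.

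Add to section 7: non-inferiority is concluded only if the upper limit of the 95% CI for the intention-to-screen 10-year risk difference in CRC mortality (FIT minus colonoscopy) is below the documented margin. Give the risk ratio to which that margin corresponds at the expected risk. Date the correction and state whether anyone involved had seen outcome data by arm.

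If the original margin cannot be documented, make no non-inferiority claim on 1.6%. Report the risk difference and risk ratio with 95% CIs.

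No new recruitment or data are needed, but this is more than a wording change. It alters the primary threshold late: section 8 has "Completion of the study: December 2021" and places the main analyses in June 2024. The corrected threshold will probably be stricter, and the non-inferiority claim may be lost if no record is found.
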